
analyses that examine FTO gene polymorphisms coupled with certain types of dietary intervention which are then associated with changes in nutritional status, body composition, and various inflammatory and hormonal biomarkers in obese subjects (Razquin et al. 2010; De Luis et al. 2012b; De Luis et al. 2015a; De Luis et al. 2015b; Luglio et al. 2017; Di Renzo et al. 2018; De Luis et al. 2020; Parastouei et al. 2020), however, some things are still unclear and limited. Apart from that, no one has ever linked the FTO gene polymorphism to the Balanced Nutrition Diet intervention which is the reference in Indonesia, as well as its effect on cardiovascular risk.
 
Research purposes:
 
General purpose:
 
Examining the Effect of a Balanced Nutritional Diet on Cardiovascular Risk Factors Among Two Types of FTO rs9939609 Gene in Obese Young Women.
 
Special purpose:
 
 1. Analyze differences in the body composition of obese young women between A allele carriers (AC) and TT allele homozygous (TH) groups after Balanced Nutrition Diet intervention 2. Analyze differences in biomarkers of inflammation related to cardiovascular risk (interleukin (IL-6), high-sensitivity CRP (hs-CRP), and adiponectin (ADP)) of obese young women between A allele carriers (AC) and TT allele homozygous (TH) groups after Balanced Nutrition Diet intervention 
Benefits of research:
 
For research subjects, subjects can find out the allele type of the FTO rs9939609 gene themselves as an illustration of genes related to obesity and that can be used as a basis for precision nutrition interventions and will receive nutritional education about balanced nutrition. For the public, it is hoped that this research can increase knowledge about consumption recommendations, especially to normalize nutritional status and reduce the risk of cardiovascular disease by improving health status, especially for young adult women. For educational institutions, it is hoped that this research will provide new scientific evidence in the field of nutrigenomics regarding the interaction of genes and diet influencing the risk of obesity and cardiovascular disease. For the government, it is hoped that it can become a reference for making a policy to reduce obesity cases in Indonesia.
 
Number of Research Subjects:
 
This research uses a hypothesis testing formula for 2 independent samples based on Sastroasmoro & Ismael (2014):
 $n_1 = n_2 = 2 \left[\frac{(Z_{\alpha} + Z_{\beta})S}{X_1 - X_2} \right]^2$ 
The results of calculations using data from previous research (De Luis et al. 2015b) resulted in 7 people. This study used 4 groups, namely 2 control groups and 2 intervention groups, adding an anticipated dropout of 50%, the total number of subjects was at least 44 people or 11 people per group.
 
Information:
 
n = minimum number of subjects
 
Z_{α} = type I error (1.96)
 
Z_{β} = type II error (1.28; power 90)
 
S = standard deviation of the two groups
 
$X_1 - X_2$ = desired clinical difference (difference in weight between Allele T and Allele A)
 
Research by De Luis et al. (2015b) is a consideration for the expected weight loss of subjects in this study, namely assuming a weight loss of ± 1 kg in A allele carriers and ± 0.35 kg in homozygous T subjects after 1 month of intervention with the balanced nutritional diet provided.
 
How to Choose Research Subjects

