--	---

	
the FTO SNP rs9939609 was associated with changes in REE adjusted for fat mass and lean mass, with the AA allele showing a decrease compared to TT.
 
Several studies have been conducted looking at the relationship between the FTO rs9939609 genotype and interleukin-6 (IL-6) levels, but only a few have shown real differences (de Luis et al. 2012b; Zimmermann et al. 2011; de Luis et al. 2016; Magno et al. 2018; Hosseini et al. 2011). Studies have also been conducted that there is an association of FTO rs9939609 with higher levels of C reactive protein (CRP) (Fisher et al. 2009; Sun et al. 2010; Lappalainen et al. 2011; Tupikowska-Marzec et al. 2019). However, other studies show contradictions (Zimmermann et al. 2011).
 
Research by Mehrdad et al. (2020a) showed that subjects with A allele carriers (AA and AT) had lower adiponectin levels than wild-type subjects (homozygous TT) with homozygous AA allele types having the lowest values although not significantly different. Several other studies also show the same thing in both obese and other types of adult subjects (Saucedo et al. 2017; Isgin-Atici et al. 2021). However, research by de Luis et al. (2016) and Duicu et al. (2016) showed a contrast, namely that adiponectin levels were lower in the TT genotype group compared to the AA genotype group. Based on what has been explained above, several outcome indicators that will be analyzed are waist-hip circumference, mass and total fat percentage &visceral, interleukin-6 levels, hs-CRP levels, and adiponectin levels.
 
Statistical analysis
 
The data obtained were tested statistically using SPSS statistical software for Windows (IBM version 26.0, SPSS Inc., Chicago, Ill., USA). The normality of variable distribution was verified with the Shapiro-Wilk test. Analysis of Variance (ANOVA) was used for all baseline data. Paired samples t-test was used to see changes in calorie intake, macronutrients, BW, BMI, waist circumference, hip circumference, waist-hip ratio, RM, percent total fat, visceral fat, subcutaneous fat, skeletal muscle, IL-6, hs-CRP, and adiponectin between before and after intervention. Data are presented as mean \pm SD and P < 0.05 was considered statistically significant.
 
c) Planned interim analysis: There is no interim analysis in this study.
 
d) Clinical trial termination procedures: Referring to the guidelines for good clinical trials in Indonesia (POM RI 2016), clinical trials are terminated if clinical trial safety problems occur, such as serious undesirable events and serious side effects of the test product. The principal investigator will report the KTDS to the ethics committee no later than 3 days after the incident is discovered. The possibility of KTDS that could occur in this study is that the patient requires hospital treatment as a result of the intervention process.
 
e) Estimated research time required for one subject per procedure: \pm4 weeks
 
f) Ethical issues (state your opinion about the ethical issues this research may encounter):
 
 • Respect for person (respect for human dignity): Subjects in this study took part based on their own conscious choice, there was no element of coercion. Subjects have the right to be protected, including that all Subject data will be kept confidential. • Beneficence(beneficial) Non-maleficence (not harmful): This research optimizes benefits and minimizes harm to subjects. The results of the research will be useful for society. The research design has been made as clear as possible. Researchers have competencies that are appropriate to the research topic to be conducted. • Justice(justice): Subjects are treated the same/or there is no differentiation between subjects.

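### The 90% power with 7 per group rests on an SD that is never printed and on a standardised difference of about 1.7 to 1.9; a t-test at 7 per group falls short of 90% even then

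*Combined protocol and SAP*

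**What the plan says.** Part B, item 1 of the protocol, under the number of research subjects, gives the usual two-sample formula n = 2[(Zα + Zβ)S/(X1-X2)]². It takes Zα as "type I error (1.96") and Zβ as "type II error (1.28; power 90"). X1-X2 is the "desired clinical difference (difference in weight between Allele T and Allele A"), and the other input is defined as "S = standard deviation of the two groups". Neither line carries a number.

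The calculation, from data of a cited earlier study, "resulted in 7 people". An anticipated dropout of 50% then takes this to 11 per group, 44 in all four groups. A separate sentence refers to the same study for the expected effect, "assuming a weight loss of ± 1 kg in A allele carriers and ± 0.35 kg in homozygous T subjects after 1 month of intervention". Under Statistical analysis (item 9b), "P < 0.05 was considered statistically significant".

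**The concern.** Every element of the calculation is printed or implied except S, so a reader cannot get from the inputs to 7. Solving backwards gives a value of S far too small to be the spread of body weight, although weight is what the definition of X1-X2 names. Either weight change was meant and the label is wrong, or the numbers entered were not those that the plan shows.

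This is the trial's only planning calculation, and both specific objectives compare A carriers with TT homozygotes. A reader who accepts 90% power could take a null genotype comparison as evidence of no difference. That inference needs a power figure that can be checked and that fits the number of women likely to finish.

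**Working it through.** **Inputs from the protocol (part B, item 1).** Zα = 1.96; Zβ = 1.28; sum 3.24. Result n = 7 per group; planned size 11 per group; anticipated dropout 50%. Expected losses are 1 kg and 0.35 kg, so the implied difference is 1 - 0.35 = 0.65 kg. The plan does not write out 0.65. S is not given.

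**Reproducing 7.** This cannot be done forwards. Solving the formula for the ratio gives S/(X1-X2) = √(n/2)/3.24.

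- n = 6: √3/3.24 = 0.535
- n = 7: √3.5/3.24 = 0.577

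The formula therefore rounds up to 7 only for a ratio above 0.535 and up to 0.577, a standardised difference of 1.73 to 1.87. With a difference of 0.65 kg:

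- lower end: S = 0.65 × 0.535 = 0.348 kg
- upper end: S = 0.65 × 0.577 = 0.375 kg

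**Sensitivity of that band.** Other conventions move it, but S stays below 0.6 kg in each variant tried:

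- one-sided 5% alpha: 0.385 to 0.416 kg
- 80% power: 0.402 to 0.434 kg
- formula without the factor 2: 0.491 to 0.531 kg
- difference of 1.0 kg: 0.535 to 0.577 kg

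**Body-weight reading.** If S were a body-weight SD of 10 kg (an assumption), n = 7 would need a genotype difference of 10/0.577 = 17.3 kg to 10/0.535 = 18.7 kg. Nothing in the plan resembles that.

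**Power inside the implied band.** The formula uses normal quantiles, which are optimistic at 7 per group. Two-sided 5% t-test power comes from the noncentral t with 2n - 2 degrees of freedom and noncentrality 0.65/(S√(2/n)):

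| Completers per group | S = 0.348 kg | S = 0.375 kg |
|---|---|---|
| 5 | 74% | 67% |
| 6 | 83% | 77% |
| 7 | 89% | 84.5% |
| 11 | 99% | 97% |

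The rows for 5 and 6 apply if half of 11 drop out (11 × 0.5 = 5.5). The planned 11 is 7 × 1.5 = 10.5 rounded up. Keeping 7 after a 50% loss would take 7/0.5 = 14 per group.

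**Power outside the band.** S is assumed, because the documents give no SD of weight change; the difference is 0.65 kg:

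| S (kg) | n per group, plan's formula | t-test power at 7 | t-test power at 11 |
|---|---|---|---|
| 0.5 | 13 | 61% | 83% |
| 0.75 | 28 | 32% | 49% |
| 1.0 | 50 | 20% | 31% |
| 1.5 | 112 | 12% | 16% |

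For example, at S = 1.0, n = 2 × (3.24 × 1.0/0.65)² = 49.7.

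**Largest S that gives 90% power for 0.65 kg.**

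| Completers per group | t-test | Plan's normal formula |
|---|---|---|
| 7 | 0.34 kg | 0.375 kg |
| 11 | 0.45 kg | 0.47 kg |

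**The case against.** The best defence is that 0.65 kg is never shown as the value entered. The 7 is said to come from an earlier study's data, and the 1 and 0.35 kg losses appear in a separate sentence about expected effect. The result fixes only a ratio: a larger difference would go with a larger S, for example 1 kg with 0.53 to 0.58 kg. This stands. A reader might infer that S must have been 0.35 to 0.375 kg, and the documents do not support that without the condition on 0.65 kg. But if another difference was entered, the 7 does not apply to the losses this trial expects.

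It can also be said that a small spread of change is not excluded. The women are aged 18 to 25, of one ethnicity and lightly active, and the diet arms receive three supplied meals a day set to individual energy needs. This stands too. No SD of 28-day change is given, so calling 0.375 kg too tight would be a judgement from outside the documents.

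Thirdly, the plan's numbers are losses, so weight change is the natural reading and the label is merely loose. That is probably so. It makes a need for thousands of subjects, computed from a body-weight SD, an unfair inference. The wording still has to be corrected, because as defined it cannot lead to 7.

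Finally, body weight is missing from the list of outcome indicators in item 9b, although the Statistical analysis paragraph tests its change. This limits how directly the power figure bears on the listed outcomes, but it does not make the figure verifiable.

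**Conclusion.** The point holds in this form: the stated power cannot be verified, and it depends on an unstated ratio that amounts to a standardised difference of about 1.7 to 1.9. By a two-sided t-test, that ratio gives 84.5 to 89% at the calculated 7 per group, not 90%. It gives 67 to 83% if the anticipated 50% dropout leaves 5 or 6 of 11. These shortfalls depend only on the ratio that 7 implies and not on the 0.65 kg. The conversion to kilograms and the table of assumed S values do depend on 0.65 kg.

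A reader might go further and conclude that the trial cannot have 90% power. The documents do not support that: at the implied ratio, 11 completers per group would give 97 to 99%. How far true power falls below this depends on an SD that the plan does not supply. The supported conclusion is that the 90% is conditional, that the condition is not stated, and that it fails at the plan's own calculated group size and after its own anticipated dropout.

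**What to change.** In the sample-size section:

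- Define X1-X2 as the difference between genotypes in 28-day weight change, and S as the SD of that change.
- Print both values, with their source in the cited study.
- Replace the single 90% figure with t-test power, or the detectable difference, over a stated range of S. Give it at 11 per group and at the number left after the anticipated dropout.
- For a difference of 0.65 kg, state that 90% power needs S of at most about 0.34 kg with 7 completers or about 0.45 kg with 11 (t-test). The plan's normal formula puts these limits at 0.375 and 0.47 kg. The number of completers must be given with each limit, because 0.375 kg is not the limit for the planned 11.

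This changes protocol wording only and needs no extra enrolment. The cost is a less favourable stated power.

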--

	
Inclusion Criteria: 1) Obese women (body fat percentage >35%) who have light physical activity based on PAL (can select prospective subjects who have participated in preliminary research to completion); 2) Sundanese ethnicity (father, mother, grandfather, grandmother originally from West Java); 3) normal fasting blood pressure and blood sugar; 4) aged 18-25 years (based on Loos and Yeo (2014) that the relationship between the FTO gene and obesity is greatest in young adulthood); 5) not currently pregnant or breastfeeding; 6) willing to participate and sign informed consent.
 
Exclusion Criteria: 1) currently pregnant and breastfeeding; 2) have a history of chronic disease; 3) regularly consume antioxidant supplements and/or phytopharmaceuticals; 4) currently participating in other research.
 
Risks that may arise and how to overcome them:
 
Potential harm to the procedure being performed is very rare. The potential that may be encountered is limited to conditions of infection and the formation of hematomas (blood clots due to needle sticks). This risk can be reduced by treatment by experienced professionals and the use of disposable equipment and aseptic procedures, as well as appropriately sized needles to minimize the occurrence of hematomas. Apart from that, there may be a danger of bacterial contamination from intervention foods made by researchers. This can be prevented by maintaining hygiene and sanitation during preparation, processing, packaging, and when providing intervention food. In addition, the possibility of side effects or dangers from consuming the dietary intervention provided is prevented by collecting data on dietary restrictions/allergies for each subject before the intervention is carried out.
									
2.	
Research Methods (There may be more than one)  Randomization
 
 Open labelled  Placebo  Cross-over  Single Blind  Treatment controlled  Parallel  Double Blinds  Others mentioned,
									

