	
be conducted using the block randomization method, based on the FTO gene allele. This process will involve two sample randomization blocks: one for A carriers allele and another for T homozygous individuals. Each block will then be randomized and divided into two groups, maintaining a 1:1 ratio between control and dietary intervention. Following randomization, four groups will be formed: two groups receiving the Balanced Nutrition Diet intervention (DAC: A allele carriers + Diet; and DTH: homozygous T allele + Diet), and two control groups (CAC: A allele carriers; and CTH: homozygous T allele). Nutrition education will be provided to all groups. The intervention period will span 4 weeks (28 days), after which a second blood draw will be conducted to gather endline data.
 
The Balanced Nutrition Diet is meticulously designed to supply the body with nutrients in suitable types and quantities, adhering to the principles of food diversity which include variety, balanced proportions, correct amounts, and consistency. Additionally, it emphasizes the "Fill My Plate" guideline, advocating for the consumption of all five food groups daily or at each meal. Portion sizes of the Balanced Nutrition Diet are structured according to the "Balanced Nutrition Tumpeng" model, encompassing 3-4 portions/day of carbohydrates, 2-3 servings/day of fruit, 3-4 servings/day of vegetables, and 2-4 servings/day of side dishes, with restrictions set at 4 tablespoons of sugar, 1 teaspoon of salt, and 5 tablespoons of oil per day, alongside a recommendation of drinking 8 glasses of water daily.
 
During the intervention period, food is provided three times a day - breakfast, lunch, and dinner - following a 28-day menu cycle. The researcher bears the sole responsibility for covering the cost of all food provided to the intervention group during this 28-day period. The Balanced Nutrition Diet offered adheres to specific macronutrient distribution ratios of 45-55% carbohydrates, 15-20% protein, and 20-25% fat, as outlined by Almatsier (2010). Complex carbohydrates, such as whole grains, are prioritized, while protein sources lean towards low-fat options, with half derived from plant-based sources. Monounsaturated and polyunsaturated fats are favored, and organic ingredients are preferred whenever possible.
 
Each meal's composition adheres to the "Fill My Plate" principle, and daily portions follow the "Balanced Nutrition Tumpeng" concept. Specifically, the diet provided by Eat & Fit Catering adheres to certain guidelines, including cooking methods that eschew fire and oil frying in favor of boiling, sautéing, or roasting techniques. Canola oil is the preferred oil, sodium-reduced salt is utilized, and mushroom stock serves as the primary flavouring agent, ensuring both healthfulness and taste. For each subject, energy requirements were calculated according to resting energy expenditure (REE) estimates using Mifflin-St. Jeor Equation (Mifflin et al. 1990). REE is then multiplied by the physical activity level (PAL) according to WHO-FAO that has been obtained.
 
REE (women)= (9.99 x Body Weight) + (6.25 x Height) + (5 x Age) – 161
 
The dietary distribution to subjects occurs three times, facilitated by couriers from the catering party. Should the delivery fall beyond the catering courier's radius, online delivery services will be utilized, with costs borne by the researcher.
 
In contrast, the control group subjects do not adhere to a specific diet regimen. However, they will receive general guidance on healthy eating habits and will be monitored closely. Nonetheless, their energy requirements will still be assessed based on REE and physical activity levels, as previously mentioned.
 
b) Determination of outcome indicators:
 
Evidence shows that compared with TT wild type, the risk allele A FTO rs9939609 showed significantly higher body weight, body mass index, waist circumference, hip circumference, and waist-to-hip ratio (Mangge et al. 2011; Tupikowska-Marzec et al. al. 2019; Mehrdad et al. According to Chrostowska et al. (2013), evidence is growing that the waist-hip circumference ratio is a stronger indicator of cardiovascular disease than body mass index. The meta-analysis of Gholamalizadeh et al. (2020), showed that carriers of the A allele of the FTO rs9939609 polymorphism had a higher fat percentage. The research results of Dorling et al. (2021) showed

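### The printed resting-energy formula adds the age term that the equation it names subtracts, so each woman's calculated REE is 180 to 250 kcal/day too high if the line is followed

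*Combined protocol and SAP*

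**What the plan says.** The rule is in Section B, item 9(a), in the account of how the diet is administered. It states that for each subject "energy requirements were calculated according to resting energy expenditure (REE) estimates using Mifflin-St. Jeor Equation", and prints a formula for women that opens "REE (women)= (9.99 x Body Weight) + (6.25 x Height) + (5 x Age", then closes the bracket and subtracts 161. The next step is that "REE is then multiplied by the physical activity level (PAL) according to WHO-FAO that has been obtained".

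Controls follow no set diet, but the same calculation covers them: "their energy requirements will still be assessed based on REE and physical activity levels, as previously mentioned". The inclusion criteria in Section B, item 1 restrict entry to women "aged 18-25 years" with light physical activity. No numeric activity level is given.

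The formula appears once. Nothing else in the document corrects it, works an example or states a calorie target.

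**The concern.** The plan does not offer a formula of its own. It names a standard one and then prints a line that differs from it in one sign. With the plus sign, calculated REE rises with age at fixed weight and height; the named equation makes it fall.

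This is the plan's only individual energy rule, and it applies to diet and control subjects alike. Anyone working from the protocol would obtain a requirement clearly above the one the named method gives. If meals were then set to that figure, the diet groups would be offered more energy than intended. The before-after changes in weight and fat in those groups could shrink as a result. Section B, item 1 expects losses of only about 1 kg in A carriers and 0.35 kg in TT women after one month, so there is little room for that.

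**Working it through.** **Inputs from the document**
- Printed formula: 9.99W + 6.25H + 5A − 161 (item 9(a)). No units are stated; kg, cm and years are taken here.
- Age limits: 18 and 25 years (item 1).
- Requirement = REE x activity level (item 9(a)).
- Intervention length: 28 days (item 9(a)).

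**Premise from outside the document**
- The women's form of the named equation is 9.99W + 6.25H − 5A − 161. This is the definition of the method the plan invokes. The document does not print it.

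**Assumptions, for illustration only**
- Light activity level 1.40 to 1.69.
- Heights 150 to 160 cm, weights up to 90 kg, and BMI above 30 as in item 7 of the case report form.

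The plan states no REE value, so there is no figure of its own to reproduce.

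**Step 1: size of the error.** Printed minus subtracting form = 5A − (−5A) = 10A, whatever the weight or height.
- Age 18: 180 kcal/day
- Age 25: 250 kcal/day

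**Step 2: one example.** At 75 kg and 155 cm (BMI 31.2), the terms without age are 749.25 + 968.75 − 161 = 1,557.

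| Age | Printed | Subtracting | Excess |
|---|---|---|---|
| 18 | 1,647 | 1,467 | 180 (12.3%) |
| 21 | 1,662 | 1,452 | 210 (14.5%) |
| 25 | 1,682 | 1,432 | 250 (17.5%) |

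From 18 to 25 the printed form rises by 35 kcal, while the subtracting form falls by 35.

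**Step 3: relative size.** Excess = 10A / (9.99W + 6.25H − 5A − 161). The activity level cancels.
- Lowest: 18 years, 90 kg, 160 cm: 180 / 1,648.1 = 10.9%
- Highest (limit): 25 years, 67.5 kg, 150 cm: 250 / 1,325.8 = 18.9%

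**Step 4: effect on the requirement.**
- Lowest: 180 x 1.40 = 252 kcal/day
- Highest: 250 x 1.69 = 422.5 kcal/day

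Over 28 days this is 252 x 28 = 7,056 to 422.5 x 28 = 11,830 kcal per woman. It would reach the plate only if the printed sign was used and meals matched the result.

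**Step 5: could the plus sign come from reading the PDF?** The minus before 161 came through on the same line. A misread of the age sign alone is therefore unlikely, though it cannot be fully excluded.

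**The case against.** The strongest objection is that the correct sign is nowhere in the document, and the source it cites cannot be seen here. No stated REE or calorie target contradicts the printed line. This stands to the extent that the sponsor should check the source before changing anything. It does not remove the point: the plan names the method, so the method's definition is the right yardstick, and every other printed term agrees with it.

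Second, the slip may be only typographical. The text says requirements were calculated with the named equation, and a reference list in the same section is garbled, so a one-character error in writing or translating is plausible. Meal portions are described by a food-guide model with fixed ranges, and the research funds table budgets a flat 45,000 rupiah per meal. Neither ties meals to REE, and neither shows that meals ignored it. This also stands: no wrong calculation and no wrong meal is demonstrated.

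Third, the percentages depend on assumed body sizes. The protocol's own criterion is body fat above 35% with no BMI limit, so the range in Step 3 is not a bound. At 60 kg, 155 cm and 25 years the excess is 250 / 1,282 = 19.5%; at 100 kg, 165 cm and 18 years it is 180 / 1,779 = 10.1%. Only the 180 to 250 kcal/day is free of body-size and activity assumptions.

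**Conclusion.** The point holds as a minor error in an operative rule. Given the sign premise, the printed formula overstates REE by 180 kcal/day at 18 and 250 kcal/day at 25. On the labelled assumptions the excess is 10.9% to 18.9%, and the daily requirement is 252 to about 423 kcal too high.

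The consequence for the trial is limited. The same formula serves A carriers and TT women, so the genotype contrast is essentially untouched. The sample size does not use REE. The plan's sentence that "several outcome indicators that will be analyzed are waist-hip circumference" and other measures does not list energy requirement, and no planned analysis compares intake with requirement. An effect on weight or fat change in the diet groups remains conditional on two facts the document does not give: the sign actually used, and whether meal energy was set to the result.

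**What to change.** Check the cited equation, then change the age term to − (5 x Age) and state the units: kg, cm and years. Recompute the requirement for every woman, diet and control, before menu energy is set. If meals have already been supplied, report which form was used and the resulting difference in requirement for each woman.

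The cost is one corrected sign, a line of units and a recalculated spreadsheet. No extra subjects, visits or staff are needed.

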	6.	How to Get Research Subjects:	 Individual contacts  Basic data from other studies  Reference  Advertisement (attach)  Others, explain		
	7.	Subject Criteria:	 Prone to  Child's age < 12 years  Prisoner  People with impaired cognitive function/unconsciousness  Pregnant mother  TNI and Police  Others, please specify:  Not Vulnerable		
8.	If this research is a clinical trial using human subjects, have pre-clinical trials/tests on animals been carried out, data on safety and efficacy from previous studies/in other countries?  No  Yes References (Name, Title, Journal): – Resume of Research Results: – Previous experience (own or others) of the action to be carried out (have clinical trials on humans been carried out, safety and efficacy data from previous studies/in other countries):  No  Yes References (Name, Title, Journal): Di Renzo L, Cioccoloni G, Falco S, Abenavoli L, Moia A, Sinibaldi Salimei P, De Lorenzo A. 2018. Influence of FTO rs9939609 and Mediterranean diet on body composition and weight loss: A randomised clinical trial NCT01890070 NCT. J Transl Med. 16(1):1–12. doi:10.1186/s12967-018-1680-7. Resume of Research Results: Randomized clinical trial examining the effects of FTO rs9939609 and the Mediterranean diet on body composition and weight loss. The results obtained show that the Mediterranean Diet is proven to be good for reducing body fat mass, while the data on the effects of FTO are still uncertain.				
9.	Clinical Trial Process a) Intervention administration (dose regimen, invasive and non-invasive procedures, comparison drugs, placebo): Following informed consent and initial screening, blood samples will be collected from all research participants to establish baseline data. Subsequently, randomization of the samples will				

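### Baseline values and the genotype stratum never enter a model of the outcomes, so a diet-versus-control comparison built on simple change would keep chance baseline imbalance and could lose precision

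*Combined protocol and SAP*

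**What the plan says.** Section B, item 9(a) provides all the data that an adjusted analysis needs. Before randomisation, "blood samples will be collected from all research participants to establish baseline data". Allocation is stratified by genotype: "This process will involve two sample randomization blocks: one for A carriers allele and another for T homozygous individuals", with diet and control at 1:1 inside each. Follow-up is a single later measurement: "The intervention period will span 4 weeks (28 days), after which a second blood draw will be conducted to gather endline data". The result is four cells, diet and control for A carriers and for TT women.

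The Statistical analysis paragraph in item 9(b) is the whole analysis plan. After a Shapiro-Wilk check it says "Analysis of Variance (ANOVA) was used for all baseline data. Paired samples t-test was used to see changes in calorie intake, macronutrients, BW"; the list of paired t-tests continues through anthropometry and body composition, ending with "skeletal muscle, IL-6, hs-CRP, and adiponectin between before and after intervention". It names no covariate, no ANCOVA or regression, no stratum term, and no between-group test of endline values or of change. It does not say how many groups the baseline ANOVA compares; four is the natural inference from the design.

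**The concern.** A baseline measurement can do useful work in a small trial: it removes chance differences between arms and absorbs part of the between-woman variation. Here it does neither.

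A significance test on baseline data is no substitute. Within a genotype, diet and control are randomised, so any baseline difference between them is chance. A P value neither corrects that difference nor shows that it is small enough to ignore. A paired t-test subtracts the baseline within each woman but compares no groups.

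The obvious repair for the missing comparison is a t-test or ANOVA on change scores. That would leave this weakness in place. Subtraction assumes that a woman who starts one unit higher ends one unit higher. When rho is below 1 she is expected to end less than one unit higher, so subtraction over-corrects. At stake is the precision of the randomised diet effect within each genotype, and of the difference between those effects, in a trial of 44 women.

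**Working it through.** **The plan's own figure.** Item 1 (Number of Research Subjects) uses n = 2[(Zα + Zβ)S/(X1 − X2)]² with 1.96 and 1.28, and assumed losses of 1 kg and 0.35 kg, so the difference is 0.65 kg. S is not given, so the 7 per group can only be back-solved. S = 0.375 kg gives 2 × (3.24 × 0.375/0.65)² = 6.99, rounded up to 7. Then 7 × 1.5 = 10.5, rounded up to 11, and 11 × 4 = 44. This calculation concerns weight compared between genotypes. It supplies neither a biomarker effect size nor a rho.

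**Inputs for the check**
- From the documents: four cells, 11 per cell, 1:1 within genotype, one baseline and one endline value; two-sided 5% (from Zα = 1.96).
- Assumed: equal SD at both visits; rho from 0.3 to 0.9; true diet effect within one genotype d = 1.0 SD of change.

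**1. Chance imbalance.** The SD of the baseline difference between two randomised cells is √(2/n) outcome SDs: √(2/11) = 0.43. For a realised imbalance D, the change-score contrast is shifted by −(1 − rho)D. For D = 0.43 the size of the shift is:
- rho 0.3: 0.70 × 0.43 = 0.30 SD
- rho 0.5: 0.50 × 0.43 = 0.21 SD
- rho 0.7: 0.30 × 0.43 = 0.13 SD
- rho 0.9: 0.10 × 0.43 = 0.04 SD

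**2. Precision.** In outcome-variance units, Var(change) = 2(1 − rho) and Var(ANCOVA) = 1 − rho². Their ratio, ANCOVA to change, is (1 + rho)/2. Estimating the slope multiplies this by about 1 + 1/(df − 1), where df is the ANCOVA residual degrees of freedom.

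**3. Power for the diet effect within one genotype, error pooled over four cells of 11.** Change scores have df = 44 − 4 = 40 and noncentrality 1.0 × √(11/2) = 2.345, so power is 63%. ANCOVA has df = 39 and slope penalty 1 + 1/38 = 1.026; its noncentrality is 2.345/√(variance ratio).

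| rho | (1 + rho)/2 | with penalty | noncentrality | power |
|---|---|---|---|---|
| 0.3 | 0.65 | 0.667 | 2.87 | 80% |
| 0.5 | 0.75 | 0.770 | 2.67 | 74% |
| 0.7 | 0.85 | 0.872 | 2.51 | 69% |
| 0.9 | 0.95 | 0.975 | 2.38 | 64% |

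Holding d at 1.0 SD of change makes the change-score power the same in every row. In outcome SDs the effect is √(2(1 − rho)), that is 1.18, 1.00, 0.77 and 0.45.

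**4. Smaller cells.** At 7 per cell, change scores have df = 24 and noncentrality √3.5 = 1.871, so power is 43%. ANCOVA (df = 23, penalty 1 + 1/22) gives 53% at rho 0.5 and 44% at rho 0.9.

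**5. Break-even.** Adjustment stops gaining precision when (1 + rho)/2 × penalty = 1. At 11 per cell this is rho = 2/1.026 − 1 = 0.95; at 7 per cell it is 2/1.045 − 1 = 0.91.

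**The case against.** The strongest objection is that the plan contains no diet-versus-control contrast, so there is no estimate for imbalance to sit in. A paired t-test compares no groups. This stands. A reader might infer that the planned diet effect is already contaminated by imbalance; the documents do not support that, because no such effect is planned. The harm is conditional on the comparison that the randomised design and the stated objectives call for. It deserves its own statement because adding a change-score test would answer the missing-comparison problem and leave this one.

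A second objection is that the gain depends on a correlation the documents do not give. This also stands. A reader might infer that IL-6, hs-CRP and adiponectin are bound to lose power. That cannot be shown: neither rho nor an effect size is given for any of them, and at rho 0.9 the gain is about one percentage point.

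A third objection concerns genotype. It is not randomised, so a baseline comparison of A carriers with TT women is not pointless, and item 9(b) itself cites expected differences between them. The criticism of baseline testing therefore applies only to diet against control. For the same reason, adjusting the A-carrier versus TT contrast for a baseline that may differ by genotype answers a different question from comparing their mean changes. The objectives in item 1 ask for exactly that contrast, so the report must say which question each result answers.

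**Conclusion.** The point holds as a conditional one. The plan collects baselines and stratifies by genotype but uses neither in a model of the outcomes. When the arms are compared on change, a share (1 − rho) of chance imbalance remains: 0.21 SD for a typical imbalance at 11 per cell and rho 0.5. At 11 per cell, baseline adjustment would raise power for the within-genotype diet effect from 63% to between 80% (rho 0.3) and 64% (rho 0.9). The gain is material at low to moderate rho, and there is essentially no loss at 0.9.

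These sizes rest on an assumed effect of 1.0 SD of change, equal variances at the two visits, a common slope, error pooled over four cells, and all 11 women per cell completing. The documents supply only the cell structure, the sample size and the type I error. The larger defect is the missing between-group and interaction analysis; this point says which model should fill the gap. It is worth acting on because it needs no new data, and because fixing the model in advance prevents a later choice among endline, change and adjusted results.

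**What to change.** In the Statistical analysis paragraph of item 9(b):

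1. State that the between-group analysis of each outcome is a linear model (ANCOVA) of the endline value, with terms for diet, FTO genotype (the randomisation stratum), diet-by-genotype and that outcome's own baseline. Use the log scale for both visits of the biomarkers if logs are adopted.
2. Report the diet effect within each genotype, and the difference between these two effects, with 95% confidence intervals.
3. Keep the paired t-tests as description of within-group change.
4. Replace the baseline ANOVA with a descriptive table by the four groups, without P values for the randomised diet-versus-control comparison.
5. State that genotype is not randomised. If a baseline-adjusted A-carrier versus TT contrast is reported, label it as a comparison of women with the same starting value, distinct from a comparison of change.

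The cost is a few sentences and one standard SPSS procedure on data already collected. The statistical price is one residual degree of freedom per model, which outweighs the gain only if rho exceeds about 0.95 at 11 per cell or 0.91 at 7 per cell.
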